5. **Low blood pressure:** Carnosine synthesized in the body has been found to decrease blood pressure via influencing the autonomic nervous system.⁴³ Hence, in theory, taking supplemental carnosine might lower blood pressure and or exacerbate lowering of blood pressure in people taking antihypertensive medications. Hence, all participants taking blood pressure lowering medication will be cautioned for this interaction and advised that in case of an episode of low blood pressure to discontinue study supplement and immediately seek medical attention from a licensed healthcare provider.
6. **Low blood sugar:** Carnosine synthesized in the body has been found to decrease blood sugar via influencing the autonomic nervous system.⁴³ Hence, in theory, taking supplemental carnosine might lower blood sugar and or exacerbate lowering of blood sugar in people taking blood sugar lowering medications. Hence, all participants taking blood sugar lowering medication will be cautioned for this interaction and advised that in case of an episode of low blood sugar to discontinue study supplement and immediately seek medical attention from a licensed healthcare provider.

Participants will be advised to continue / discontinue after a review by the study physician and the DSMB.

[figure not shown]

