The DSMB will use a combination of, notifications, event specific reports, and scheduled cumulative trial reports to keep the EC and the IRB informed about real and potential safety issues.

Notifications

Notifications are comprised of an email to the EC and DSMB with available information on the date and nature of the event, the study physician’s evaluation of the severity, expectedness, and relatedness to study supplement; and the assessment of the event given the information known at the time of the initial reporting.

Event Specific Reports

Event specific reports are formal written reports providing the details of the event (including circumstances surrounding the event, laboratory testing, concomitant medications, and any formal diagnoses made via medical intervention). These reports include a full assessment by

the study physician of the severity, expectedness, and relatedness to study supplement as well as any available status update on the participants.

Scheduled Cumulative Trial Reports

Scheduled cumulative trial reports will be prepared semi-annually by the study PI. These will be used by the DSMB to assess recruitment, subject safety, and continued trial feasibility. These reports include total numbers of AE/SARs and SAE/SSARs experienced in the overall trial. The information provided includes both new events reported since the last DSMB meeting and cumulative events reported during the life of the trial.

CTU Reporting Requirements to DSMB and IRB

Once the event has been reported to the PI or the study physician, it will be reported to the Executive Committee within 48 hours. The UofL CTU (part of the EC) will use the Medical Dictionary for Regulatory Activities (MedDRA) System Organ Classes (SOC) to classify all AEs/SARs (including SAEs/SSARs assessed by PI or study physician). Additional supporting documentation may be requested from the PI and study team to enable the UofL CTU to accurately assess the event for reporting.

Reportable Events:

All unexpected events, all events related to study product, and all events with a severity grade of 3 or higher are reported by the UofL to the DSMB and the IRB.

Reporting Timeframe:

[figure not shown]
For events which are unexpected AND associated with study supplement, the CTU will notify the IRB and DSMB within 72 hours of learning of the event; with an event specific report filed no later than 7 days post notification.

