For all other reportable events, the CTU will notify the IRB and DSMB no later than 15 days of learning of the event; with an event specific report filed no later than 30 days post notification.

Cumulative trial reports (which include all events) will be generated for review by the CTU and DSMB at semi-annual DSMB meetings.

Reporting Requirements to the FDA

Carnosine is a freely available over the counter dietary supplement in the market. This is not an experimental drug or an untested product. Commercially available Carnosine (or beta-alanine) is well known in the market and it is generally recognized as “safe when used in accordance with good manufacturing practice”. The goal of this study is to provide dietary supplementation of a naturally occurring amino acid inside the body and to study whether dietary supplementation can enhance normally occurring physiological/biochemical processes in the body.

As per the Office of Inspector General of the Department of Health and Human Services' report on "Dietary Supplement Labels: Key Elements" – "The Dietary Supplement Health and Education Act of 1994 (DSHEA) ⁴⁴ defines the term "dietary supplement" to mean a product (other than tobacco) intended to supplement the diet that bears or contains one or more of the following dietary ingredients: a vitamin, a mineral, an herb or other botanical, an amino acid, a dietary substance for use by man to supplement the diet by increasing the total dietary intake, or a concentrate, metabolite, constituent, extract, or combination of any of the aforementioned ingredients". ⁴⁷ As per the DSHEA, dietary supplements are not regulated by the FDA other than for their good manufacturing practices. ⁴⁴

Hence, the study (EC or DSMB) has no obligations to report any findings to the FDA. The study will however take every precaution to ensure that the supplement providers (bulk supplier and pharmacist) are operating in facilities at par with good manufacturing practices and are in possession of appropriate certifications and licensure. These documents can be found in Appendix D.

Guidelines for Canceling Study Supplement Administration

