The events listed below will follow the same reporting criteria for SAE/SSARs as it relates to the PI as well as the CTU and are to be considered sufficient to halt the study procedure. If subject develops any of the following conditions within 48 hours of planned supplement consumption, study supplement delivery will be halted in that particular participant:

[figure not shown]
1. Diarrhea / Vomiting / Stomach Upset
2. Sudden drop in blood pressure
3. Sudden drop in blood sugar
4. Hemodynamically unstable

Holding Rules

The expected number of SAE/SSARs in this trial is anticipated to be too small to support formal statistical stopping rules. However, the following criteria are provided as guidelines under which this **clinical trial may be put on hold pending a detailed investigation by the DSMB**. The assessment of the event shall include the relationship to the trial procedures as unrelated or possibly related. If possibly related, an indication of causality to a specific aspect of the study supplement / procedures will be determined: (e.g. study supplement consumption related, study supplement safety related, study supplement manufacturing related).

Holding Criteria

The DSMB will recommend putting the trial on hold as soon as it is notified of **one or more of holding criteria** listed below. The study holding criteria have been created under the guidelines of current literature data and the 21 CFR code of the FDA regulatory information. The study holding criteria:

1. 20% or more cases of out of the total enrollment with Diarrhea / Vomiting / Stomach Upset
2. 20% or more cases of out of the total enrollment with Sudden drop in blood pressure
3. 20% or more cases of out of the total enrollment with Sudden drop in blood sugar
4. 20% or more cases of out of the total enrollment with Hemodynamically unstable events
5. 20% or more cases of out of the total enrollment with Hospitalizations
6. Or any other reason specified by the DSMB, study EC, bulk supplier or manufacturing pharmacist

As soon as any of the above is identified, the EC will inform the IRB and the DSMB. In addition, the DSMB will monitor the distribution of all SAE/SSARs, and the PI will be responsive to all DSMB concerns regarding SAE/SSARs that are not part of holding criteria listed above.

In addition, the DSMB may also recommend stopping the trial for the performance-related issues that would prevent the study from meeting its scientific objectives, such as:

[figure not shown]

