Participants who are taking antihypertension medications at the time of the study may be susceptible to a temporary sudden drop in blood pressure; during which time the participant may be at an increased risk of stroke and heart attack. The participant will be advised to inform the research team immediately of any symptoms of dizziness, light-headedness, chest pain, chest tightening, nausea, blurred vision, slurred speech, facial drooping, decrease sensations anywhere on your body, or weakness or a decrease in strength of the arms or legs. The participant will be closely monitored if started back on the study supplement regimen. The study physician will conduct a detailed assessment and provide its recommendations to the PI.

Adequacy of Protection Against Risks

The precautionary measures mentioned in the last two sections will minimize the risk associated with taking study dietary supplement. Overall the study procedures are low risk and in previous similar trials there was no complications related to Carnosine or placebo supplementation in healthy participants.^{34, 37}

Potential Benefits of the Proposed Research to the Participants and Others

The potential benefits of this research for participants include reduced oxidative stress from PM_{2.5} pollution which will have therapeutic effects such as decrease in CVD progression and ultimately decreased CVD mortality. This project will also provide mechanistic insight into Carnosine supplementation which will be useful for finding new treatments for other diseases.

Risk Benefit Analysis

The supplementation of dietary Carnosine offers a new option to participants with existing CVD of different intensities. The goal of this supplementation is to improve ameliorate the progressive nature of CVD by facilitating the reduction of oxidative stress on vasculature. Having highly trained experts oversee the supplementation with close study monitoring substantially reduces the likelihood of AEs. The potential risks to the participants remain reasonably low in relation to the possible benefit of improving their CVD risk factors during high pollution season, without the involvement of prescription medications or invasive diagnostic / treatment procedures.

Importance of Knowledge to be Gained

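### The CTU's deadline for telling the DSMB ignores seriousness, so a death or life-threatening event may be notified up to 15 days after the CTU learns of it unless it is judged both unexpected and supplement-related

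*Combined protocol and SAP*

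**What the plan says.** **The two deadlines (Section 14, Reporting Timeframe).**

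- Fast track: "For events which are unexpected AND associated with study supplement, the CTU will notify the IRB and DSMB within 72 hours". The CTU's full report is then due at most a week after that notice.
- Slow track: "For all other reportable events, the CTU will notify the IRB and DSMB no later than 15 days of learning of the event". Here the full report may follow up to 30 days after the notice.

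**What is reportable (Section 14, Reportable Events).** An event qualifies if it is unexpected, or related to the product, or of grade 3 or higher. Grade therefore decides whether an event is reported, not how fast. Seriousness, as Section 13 defines it, appears in neither rule.

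**References to a rule for serious events.**

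- Section 14 (Guidelines for Canceling Study Supplement Administration) says that the listed halt events "will follow the same reporting criteria for SAE/SSARs as it relates to the PI as well as the CTU".
- Section 13 (Unanticipated Problems) sends those problems to SAE/SSAR guidelines said to stand above it.

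**Other time limits.**

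- Section 13 (Reporting by Principal Investigator) sets 24 hours for the PI when a serious event is not known immediately. It names no DSMB recipient; that section opens by describing reporting to the PI or the Executive Committee.
- Section 14 (CTU Reporting Requirements) requires events to reach the Executive Committee within 48 hours. Section 11 describes that committee as the PI, the study physician and the CTU.

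**The concern.** The DSMB is asked to watch the distribution of all serious events and to recommend whether the trial continues. The route that takes a single event to it is sorted by two judgements, expectedness and relatedness. Neither measures how grave the event is. A fatal event that is unexpected but judged unrelated fails the two-part test. So does a life-threatening event judged related but expected.

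Such cases are foreseeable here. Section 9 admits participants with controlled hypertension or diabetes. Section 16 lists a drop in blood pressure as a possible risk and says, of participants on antihypertensive drugs, "during which time the participant may be at an increased risk of stroke and heart attack". Section 15 has grade 3 and 4 events counted after each person is enrolled, and a 15-day lag limits any part the DSMB could play in that count.

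A CTU that follows the text has nothing else to apply. It is referred to criteria for serious events that are not written down, so it must fall back on the 15-day rule.

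**Working it through.** **Inputs.** All come from Section 14, Reporting Timeframe: 72 hours and 7 days for the fast track; 15 days and 30 days for the slow track. Each first limit runs from the CTU learning of the event, and each second limit runs from notification.

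**Step 1. Longest time from CTU awareness to full report.**

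- Fast track: 72 h = 3 days; 3 + 7 = 10 days.
- Slow track: 15 + 30 = 45 days, with first notice by day 15.
- If the CTU learns only through the 48-hour step to the Executive Committee, 2 days are added, counted from the report to the PI or study physician: 12 and 47 days.

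**Step 2. Which track each kind of event takes.** Apply the two-part test to a death or life-threatening event. Such an event is grade 4 or 5 and so is reportable.

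| Judged | Notice to DSMB by | Full report by |
|---|---|---|
| Unexpected and related | day 3 | day 10 |
| Unexpected, unrelated | day 15 | day 45 |
| Expected, related | day 15 | day 45 |
| Expected, unrelated | day 15 | day 45 |

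Three of the four combinations take the slow track. The two unrelated rows do so whatever is decided about expectedness.

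**Step 3. Search for a CTU time limit for serious events.**

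- Section 13, Unanticipated Problems: refers to guidelines above it, but no CTU limit for serious events precedes it.
- Section 13, PI reporting: 24 hours, DSMB not named.
- Section 14, Executive Committee step: 48 hours, ends at that committee.
- Section 14, halt events: refers to criteria for the CTU and gives none.
- Section 14, Reporting Timeframe: the two limits above, neither tied to seriousness.

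No such limit is stated.

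**Step 4. Who decides expectedness.** Section 14 (Notifications) leaves it to the study physician's evaluation and gives no definition. The only definition of unexpected is in Section 13 under Unanticipated Problems. It lets an event be unexpected in kind, in severity or in how often it occurs. For a severe form of a named risk, the track therefore depends on a judgement that Section 14 does not anchor.

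**Step 5. Whether the holding criteria close the gap.** Items 1 to 5 in Section 14 (Holding Criteria) each need at least 20% of total enrollment: 0.20 × 400 = 80 participants, or 0.20 × 240 = 48 if enrollment is read as 240. A single serious event triggers none of them. Item 6 is open-ended but discretionary.

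**The case against.** **The DSMB may hear much sooner.** The 15 and 30 days are outer limits. The Executive Committee, which includes the CTU, knows within 48 hours and may act under item 6. Once a holding criterion is identified, that committee informs the IRB and DSMB without a 15-day wait. Section 14 also halts supplement delivery in an affected participant for the listed events. All of this stands. It makes prompt notice of a single serious event possible but does not require it.

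**A reader might infer that every named risk is expected, so that a severe hypotensive event must take the slow track.** The documents do not support that. Section 13's definition includes severity, and low blood sugar is raised only as a theoretical effect. A life-threatening form could be judged unexpected and go on the fast track. The inference is strongest for stroke or heart attack after a blood pressure drop, because both are named, and even there it remains a judgement. Nor does a related minor rash make a fair contrast: rash is itself a listed local reaction in Sections 9 and 10.

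**A reader might infer that a hold is delayed by 15 days.** The DSMB's duty to recommend a hold follows notice of a holding criterion, and items 1 to 5 are enrollment-wide thresholds with their own immediate route.

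**A reader might set 45 days beside the 84-day course (12 × 7), or turn 15 days into a number of participants enrolled meanwhile.** The 45 days run from CTU awareness, not from the first capsule, and first notice is still due by day 15. Any participant count depends on an assumed uniform intake and on the season's size: the plan gives both 400 randomized in all and a goal of 120 per year, and allows several years. Neither figure is used here.

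**A reader might see a conflict with Section 10**, which says "Participants will be advised to continue / discontinue after a review by the study physician and the DSMB". That sentence sets no deadline, and Section 9 says only that the study physician may consult the DSMB. It does not contradict the 15-day limit.

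**Conclusion.** The point holds as a gap in the reporting rule and should be fixed. A death or life-threatening event that is not judged both unexpected and related may be notified to the DSMB up to 15 days after the CTU learns of it and fully reported up to 45 days after, against 3 and 10 days on the fast track. Separately, Sections 13 and 14 rely on SAE/SSAR reporting criteria for which no CTU time limit is stated.

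This rests on reading the two deadlines as the CTU's complete rule, since no other is given, and on taking the stated limits as maxima. It needs no assumption about event rates. For an event judged unrelated it needs none about expectedness either. For a severe form of a named risk, the conclusion is only that the slow track is permitted, depending on the study physician's call. The documents do not show that serious events will in practice reach the DSMB late.

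**What to change.** 1. In Section 14 (Reporting Timeframe), put every event that meets Section 13's SAE/SSAR definition, and every grade 4 or 5 event, on the existing 72-hour notification and 7-day report track, regardless of expectedness or relatedness. Leave the two current tracks for non-serious events.
2. State in Section 14 that unexpected has the meaning given in Section 13 under Unanticipated Problems.
3. Reconcile the references in Section 13 (Unanticipated Problems) and Section 14 (Guidelines for Canceling Study Supplement Administration) with this rule, and say which reporting deadline applies to halt events that are not serious. Simply pointing all halt events to the new rule would put every stomach upset on the fast track. With 400 enrolled, up to 79 participants could have diarrhea, vomiting or stomach upset before the 20% criterion of 80 is met.

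The change affects reporting only, not supplement use or clinical care. It costs protocol wording and a small number of earlier CTU notifications and reports, since Section 14 (Holding Rules) expects few SAE/SSARs.

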15. STATISTICAL PROCEDURES

Randomization

Randomization to Carnosine assignment will be conducted using a statistical software by one of the study statisticians. The randomization key detailing which participant is in which group (Carnosine or placebo) will be maintained by the Randomization Committee (RC) consisting of the study physician ([name]) and a member of the UofL CTU. After the investigator or research coordinator verifies that screening testing is complete and the inclusion and exclusion criteria for the study have been satisfied, an un-blinded member of the Randomization Committee will have secured access to the participant's supplement assignment.

Participants will be randomized to the Carnosine or placebo group, using a block size of 6. The stratification factors are sex, age (two group) and carnosine level (two group). When a participant is identified from the screening process (data from Visit # 1), the clinical recruitment team will be informed whether the participant will be receiving supplements from pill-box labeled "A" or "B. The clinical recruitment team will assign the participant a study ID from a pre-defined series, which will have no bearings on supplement randomization process.

As detailed in Section 11 "Study Supplement", the University of Colorado Skaggs School of Pharmacy and Pharmaceutical Sciences will ship 28-day pill-boxes (total 3 per participant) pre-filled with either Carnosine or placebo. These boxes will also be pre-labeled with large sized visible letters "A" or "B". The entire study team, excluding the Randomization Committee, will be blinded to whether "A" or "B" series contains Carnosine versus placebo. The University of Colorado, Skaggs School of Pharmacy and Pharmaceutical Sciences personnel will ensure that there is absolute consistency in the contents of each series of labeled boxes. The University of Colorado Skaggs School of Pharmacy and Pharmaceutical Sciences will directly and securely transmit the randomization key and other relevant information to the Randomization Committee (study physician and UofL CTU).

Participants of both the groups ("A" or "B") will undergo the exact same procedures of data collection as detailed in section 10 "Study Visits". The CTU will monitor participant recruitment by providing reports to the study co-PI and DSMB as appropriate during the recruitment phase. Updated reports will be maintained on an Internet site accessible to all units of the study. The recruitment reports will provide data on recruitment of women and minorities (African-Americans, Hispanics, and Asians). Goals for recruitment will be set and will be reviewed by the PI.

Statistical Analyses

Biostatisticians at the Envirome Institute, with the assistance of bioinformatics experts, have adapted or developed a number of statistical programs for analyzing study data. Data are analyzed for both data monitoring purposes, as described above, and for the purpose of detecting effects of the supplement. The Envirome Institute uses standard statistical packages such as SAS, S-PLUS, R and Stata to perform statistical analyses.

Participants receiving supplementation will be presented. Participants receiving supplementation who are found not to have fully met the eligibility criteria will also be presented. On-study protocol violations will also be presented. Participants who do not complete the required observations will be listed and evaluated separately as necessary. Reasons for study discontinuation and date of withdrawal from study will be presented.

Baseline Analyses

Although the stratified random assignment of participants to the various supplements should ensure comparability with respect to known and unknown variables, imbalance may occur by chance. Descriptive statistics for baseline characteristics known or suspected to be associated with outcomes will be prepared for the various supplementation groups. The variables considered in such a description can be categorized as: 1) demographic characteristics; 2) medical history; 3) physical examination; and 4) laboratory data. Exact testing for categorical variables and Student *t* testing for continuous variables will be used to evaluate the differences in baseline variables between supplement groups.

Outcome Analyses

Primary and Secondary Endpoints

There are 5 primary endpoints: difference in EPCs (EPC-2, EPC-3, EPC-4, EPC-7, and EPC-8) between Carnosine and placebo groups at 6 weeks and 12 weeks. These endpoints will be evaluated at the alpha=0.01. There are four secondary endpoints: difference in EPCs between Carnosine and placebo groups at 12 weeks, difference in EPCs between Carnosine and placebo groups at 6 weeks, difference in arterial stiffness between carnosine and placebo groups at 6 and 12 weeks, difference in endothelial microparticles between carnosine and placebo groups at 6 and 12 weeks, and difference in platelet monocyte aggregates between carnosine and placebo groups at 6 and 12 weeks.

Continuous variables will be presented by summary statistics (such as mean, median, standard error, range, 95% CI, correlations) and the categorical variables by frequency distributions (frequency counts, percentages and 95% CI). We will also calculate correlations along with confidence intervals. To identify significant differences due to intervention, we will compare the differences using a two sample t-test. We will use regression (logistic or linear) to model and test the effect of other covariates such as age and race. We also will compare outcome measures using GLM and MIXED model procedures to account of repeat observations. General statistical analyses will be performed with the SAS statistical software package (SAS Institute Inc., Cary, NC).

Statistical Monitoring Rule

[figure not shown]
Safety monitoring of the accumulated outcomes data is designed to ensure the continuing safety of the currently enrolled participants and participants not yet enrolled. This is achieved by stopping the trial early to reduce the number of participants exposed to a harmful or ineffective supplementation.

Monitoring Non-efficacious Supplementation (Futility)

We do not plan any interim analyses for futility due to longer follow-up (1 year).

Monitoring Toxic Supplementation (Safety)

The cumulative number of grade 3 or 4 toxic events will be monitored after each person is enrolled ⁴⁸. If the cumulative number of toxic events produces enough evidence to conclude that the true toxicity rate is greater than or equal to 33% ($Pt_0 = 0.33$) then the trial will be stopped early for safety reasons. If the cumulative number of toxic events after person is treated is greater than or equal to the associated boundary value b_i then the combination supplementation is rejected for safety considerations (monitoring table with these boundaries will be generated using Ray and Rai, 2011)⁴⁸. With this rule, there is only a 5% chance of stopping the trial early for lack of safety if the true toxicity rate is less than 33%. Continual assessment of the toxic events ensures we do not expose an undue number of participants to a harmful supplementation.

A second sub-analysis to be executed is the effect of Carnosine supplementation in participants with cardiovascular disease compared to the effect of Carnosine supplementation in participants without any cardiovascular disease.

Subgroup Evaluations

The effect of subgroup stratum on the relationship between carnosine supplementation and the endpoints (both primary and secondary) will be assessed. If a carnosine supplementation effect is demonstrated, it is not likely to behave identically among all important subgroups. The subgroups of interest are age, sex, race, socioeconomic status, diabetes, smoking, hypertension, and cardiovascular disease risk scores.

These additional analyses can sometimes be helpful in identifying extreme differences in the effects of supplementation among subgroups, although the literature wisely warrants that caution be used in interpreting subgroup analyses.

Additional Analyses

We will use the 6 week and 12-week EPC levels to assess the change of EPCs from baseline to 6 weeks and 12 weeks, assessing if this trajectory is related to carnosine supplementation using mixed model analysis of variance.

We will evaluate the relationship among the indices of the primary endpoint – EPCs. Specifically, we will assess the relationship between the differences in EPCs, adjusting for important baseline covariates.

[figure not shown]
Multiple Comparisons

In this study, no adjustments have been made for multiple comparisons. Measures of effect will be effect size, the standard error of the effect size, the 95% confidence interval for the effect size and the *p*-value. *P*-values will be interpreted at nominal 0.05 levels.

